	Corticosteroid taper (dosage)	≥ 50% reduction	< 50% reduction or ≥ 5 mg increase for less than 2 weeks	≥ 5 mg increase for more than 2 weeks

^aAbsolute change of predicted percentage.

Subject tolerating Acthar Gel (or placebo) will be categorized according the following scoring:

- Response is defined as scores of ≥ 3/6 points.
- Partial Response is defined as scores of 2/6 points or stable with a reduction in corticosteroid dose (ie, a total score of +1 due to ≥ 50% reduction in corticosteroid dose).
- Nonresponse is defined as scores of ≤ 1/6 points without significant corticosteroid taper (stable or deterioration in corticosteroid response).

2. PFT.
3. Imaging: HRCT; CXR (including Scadding Score).
4. Corticosteroid tapering.

5. Physician Global Assessment.
6. Patient reported outcomes (King's Sarcoidosis Questionnaire, Fatigue Assessment Scale, and Patient's Global Assessment).
7. Symptom Assessment (Medical Research Council Dyspnea Scale, Leicester Cough Questionnaire, and steroid toxicity questionnaire).
8. Functional testing: 6MWT (including Borg Scale)
9. Extra pulmonary response (ePOST score).
10. Biomarkers, (eg, for genetic testing; optional).
11. WPAI.

Endpoints:

The endpoints for this study are:

- STS response rate at 24 weeks (Visit 8).
- STS response rate at 48 weeks (Visit 11).
- Physician and subject independent responses to the question “Would you choose to continue current treatment?” at 24 and 48 weeks.
- Time to response as evaluated at earlier time points (Weeks 4 to 20), as determined by the investigator based on clinical judgment and the following parameters:
 - Patient reported outcomes.
 - Corticosteroid tapering.
 - Patient Global Assessment.
 - Physician Global Assessment.
 - PFT (at applicable time points).
 - Extrapulmonary response (ePOST).
 - Supportive efficacy endpoints per applicable time points:
 - Six-minute walk test.
 - Symptom relief (Leicester Cough Questionnaire, Medical Research Council Dyspnea Scale, steroid toxicity questionnaire).
 - CXR (including Scadding score).
- Percentage change in overall DLCO.
- Percentage of subjects with improvement in DLCO of $\geq 5\%$; $\geq 10\%$; and $\geq 15\%$.
- Percentage change in overall FVC.
- Percentage of subjects with improvement in FVC of $\geq 5\%$; $\geq 10\%$; and $\geq 15\%$.
- Percentage of improved/stable/deteriorate - side by side comparison of HRCT based on a 5-point Likert score: much worse; worse; unchanged; better; much better (central reader).

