7.2.1. Sarcoidosis Treatment Score

This is a newly developed composite score that combines the results of PFT, chest imaging, quality of life, and changes in corticosteroid dosing as recommended by the WASOG task force ([Baughman et al., 2015](#)) and based on the results of the Acthar Gel prospective study; ([Baughman et al., 2017](#)). Individuals may score from -6 to +6. Higher scores indicate improvement.

Assessments and treatment scores categories are presented in [Table 2](#).

Table 2: Determining the Sarcoidosis Treatment Score

	Parameter	Improved	Unchanged	Deteriorate
Category of Assessment		+1	0	-1
PFT ^a	FVC	$\geq 5\%$	$> -5\% \text{ to } < 5\%$	$\leq -5\%$
	DLCO	$\geq 5\%$	$> -5\% \text{ to } < 5\%$	$\leq -5\%$
Imaging	HRCT	Improved	Unchanged	Worse
Quality of Life	King's Sarcoidosis Questionnaire (General Health)	≥ 4	$> -4 \text{ to } < 4$	≤ -4
	Fatigue Assessment Score	≤ -4	$> -4 \text{ to } < 4$	≥ 4
	Corticosteroid taper (dosage)	$\geq 50\%$ reduction	$< 50\% \text{ reduction or } \geq 5 \text{ mg increase for less than 2 weeks}$	$\geq 5 \text{ mg increase for more than 2 weeks}$

^a Absolute change of % predicted.

Subject tolerating Acthar Gel (or placebo) will be categorized according the following scoring:

- Response is defined as scores of $\geq 3/6$ points.
- Partial Response is defined as scores of $2/6$ points or stable with corticosteroid reduction (ie, a total score of $+1$ due to $\geq 50\%$ reduction in corticosteroid dosage).
- Non Response is defined as scores of $\leq 1/6$ points without significant corticosteroid taper (stable or deterioration).

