11. PROCEDURES

The schedule of study procedures is summarized in the Schedule of Events ([Table 1](#)).

If the subject is unable to come to the study site for any visit after the Baseline visit, all procedures that can be completed remotely (eg, by telephone) will be conducted as scheduled.

Collect as much information as possible, including but not limited to, AE information, new concomitant medications and changes in existing therapy, corticosteroid use, compliance with investigational therapy. Complete applicable physician assessments, PFT tests, subject-reported outcomes and assessments, 6MWT, ECG, imaging and laboratory tests at the next planned study visit as unscheduled procedures, if not already scheduled for that particular study visit.

Changes in study visit schedule, missed visits, and procedures will be captured in the eCRF.

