3.1. Overall Study Design and Plan

This is a Phase 4, multicenter, randomized, double-blind, placebo-controlled exploratory study evaluating the efficacy and safety of Acthar in the treatment of pulmonary sarcoidosis. The study will have 3 phases: screening (up to 28 days); double-blind treatment (Visit 2 to Visit 8, 24 weeks); and an optional open-label extension (Visit 9 to Visit 11, 24 weeks). A follow-up visit will be conducted at 4 weeks (\pm 2 days) after the last dose of investigational medicinal product (IMP) is administered.

[figure not shown]
An overview of the study is presented in [Figure 1](#).

Subjects who meet all eligibility criteria will be randomly assigned to receive either 1 mL (80 U) of Acthar or 1 mL of a matching placebo subcutaneously (SC) twice weekly. Following the completion of the double-blind phase, subjects will be invited to continue participation in an optional Open-label Extension Phase (Visit 9 to Visit 11, 24 weeks). Subjects who decline participation in the open-label extension phase, or those ineligible, will have their End-of-Treatment visit during Visit 8.

Dose reduction of 50% may be implemented once during the study if a subject meets one of the prespecified safety criteria (refer to protocol Section 9.1). Once dose reduction is implemented, subjects will remain on the 40 U or matching placebo twice weekly for the remainder of the study.

The schedule of study events is presented in [Appendix 15.3](#).

Figure 1: Study Overview

Note: Visit 8 is the primary efficacy evaluation time point. Additional analyses of long term efficacy and safety of subjects participating in the Open-label Extension Phase will be conducted at the completion of Visit 12. PFT and sample collection for assessment of biomarkers will be performed every 12 weeks. HRCT will be performed at Screening (Visit 1) and every 24 weeks thereafter (Visits 8 and 11).

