9.1. Sarcoidosis Treatment Score (STS)

STS is a newly developed composite score that combines the results of PFT, chest imaging, quality of life, and changes in corticosteroid dosing. Individuals may score from - 6 to + 6. Higher scores indicate improvement. Subjects tolerating Acthar Gel (or placebo) will be categorized as Response, Partial Response, and Non Response. STS can be determined by using the assessments categories as presented in table below.

Table 1: Determining the Sarcoidosis Treatment Score

	Parameter	Improved	Unchanged	Deteriorate
Category of Assessment		+1	0	-1
PFT ^a	FVC	$\geq 5\%$	> -5% to < 5%	$\leq -5\%$
	DLCO	$\geq 5\%$	> -5% to < 5%	$\leq -5\%$
Imaging	HRCT	Improved	Unchanged	Worse
Quality of Life	King's Sarcoidosis Questionnaire (General Health)	≥ 4	> -4 to < 4	≤ -4
	Fatigue Assessment Score	≤ -4	> -4 to < 4	≥ 4
	Corticosteroid taper (dosage)	$\geq 50\%$ reduction	< 50% reduction or ≥ 5 mg increase for less than 2 weeks	≥ 5 mg increase for more than 2 weeks

^aAbsolute change of % predicted.

Subject tolerating Acthar (or placebo) will be categorized according the following scoring:

- Response is defined as scores of $\geq 3/6$ points.
- Partial Response is defined as scores of $2/6$ points or stable with corticosteroid reduction (ie, a total score of +1 due to $\geq 50\%$ reduction in corticosteroid dosage).
- Non Response is defined as scores of $\leq 1/6$ points without significant corticosteroid taper (stable or deterioration).

An STS responder is defined as a subject who has an assessed STS category of Response or Partial Response at 24 weeks (Visit 8) during double-blind treatment phase and at 48 weeks (Visit 11) during open-label phase.

The descriptive statistics for developed STS scores, number and percentage of subjects in each STS response category (response, partial response and non response) will be provided at both 24 weeks (Visit 8) and 48 weeks (Visit 11). At 24 weeks (Visit 8) during double-blind treatment phase, the proportions of STS responder (defined as response or partial response) and non-responder, and corresponding odds ratio will be calculated. The 95% confidence interval (CI) of the odds ratio will be calculated as well based on asymptotic method. Pearson's chi-square test (or Fisher's exact test if any expected count is less than 5) will be used to assess the comparability between treatment groups for the STS responder

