vs. non-responder rate. At 48 weeks (Visit 11) during open-label phase, the proportions of STS responder and non-responder along with 95% CI will be provided. The 95% CI will be calculated by using the exact (Clopper-Pearson) method.

Missing STS scores will be imputed at 24 weeks (Visit 8) during double-blind treatment phase. Last observation carried forward (LOCF) method will be employed to impute missing component(s) if any component of STS is missing at the post-baseline visit during double-blind treatment phase. If there is still missing component(s) after applying LOCF imputation method, STS score will remain as missing. Subjects who do not provide data (after component level LOCF imputation) to allow classification as responders will be considered non-responders, that is, missing data will be imputed as non-responder. The same missing data imputation method will be applied to other similar efficacy endpoints in double-blind treatment phase. No imputation will be applied to the open-label extension phase. A bar plot of STS category will be provided at 24 weeks (Visit 8) during double-blind treatment phase and at 48 weeks (Visit 11) during open-label phase, respectively.

Sensitivity analyses with using only the observed data will be performed for the above analysis at 24 Weeks (visit 8) only.

Subgroup analyses by sex, race and ethnicity will be performed in similar manner as specified above on the imputed data only.

STS component scores including FVC % Predicted Score, DLCO % predicted Score, HRCT Score, King's Sarcoidosis Questionnaire (KSQ) General Health Score, Fatigue Assessment Score and Corticosteroid Taper Score will be summarized. Number and percentage of subjects in each category (Improved, Unchanged and Deteriorate) of each STS component score presented in Table 1 will be provided at 24 weeks (Visit 8) and at 48 weeks (Visit 11). Pearson's chi-square test (or Fisher's exact test if any expected count is less than 5) will be used to assess the comparability between treatment groups for each STS component at 24 Weeks (visit 8) only.

Listings of STS components and STS scores will be provided by study phases. Subjects with any missing component of STS will be indicated.

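### SAP 9.1, read literally, codes a subject with no Week 24 HRCT as an STS non-responder even when the other five components already settle that the subject is a responder

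*SAP*

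**What the plan says.** The STS sums six components, each scored -1, 0 or +1 (Protocol 7.2.1, Table 2; SAP 9.1, Table 1). The protocol gives the range: "Individuals may score from -6 to +6".

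For the Week 24 comparison, SAP 9.1 states: "An STS responder is defined as a subject who has an assessed STS category of Response or Partial Response at 24 weeks (Visit 8"). Response needs a total of 3 or more. The protocol synopsis adds: "Partial Response is defined as scores of 2/6 points or stable with a reduction in corticosteroid dose", explained there as a total of +1 that is due to a steroid reduction of at least 50%.

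Missing data in the double-blind phase are handled in steps, all in SAP 9.1:

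1. "Last observation carried forward (LOCF) method will be employed to impute missing component(s) if any component of STS is missing at the post-baseline visit".
2. "If there is still missing component(s) after applying LOCF imputation method, STS score will remain as missing".
3. Non-response is then given to subjects whose data, after carrying forward, are not enough to class them as responders. The sentence closes with "that is, missing data will be imputed as non-responder".

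On scan timing, the note to SAP Figure 1 says "HRCT will be performed at Screening (Visit 1) and every 24 weeks thereafter (Visits 8 and 11"). Protocol 11 lets a subject who cannot attend catch up on "imaging and laboratory tests at the next planned study visit as unscheduled procedures".

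**The concern.** Carrying forward works for five of the six components, because each is planned before Visit 8: lung function at Visit 5, and the two questionnaires and the steroid dose at every post-baseline visit. HRCT is different. Its score is a side-by-side change rating, and the only planned double-blind rating is at Visit 8. If that scan is missed there is normally nothing to carry forward, step 2 leaves the whole STS missing, and step 3 turns it into a failure.

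Non-responder imputation is reasonable when the outcome is unknown. Here, for some subjects, the missing item cannot change it. The rule is also uneven. A questionnaire answered at Week 4 may be carried to Week 24 and counted, while a subject with five actual Week 24 values and no scan fails.

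The endpoint matters: Visit 8 is the primary efficacy time point (SAP 3.1) and the Week 24 STS response rate is the first endpoint listed (SAP 3.2.1). The observed-data sensitivity analysis does not repair the rule, since a subject without an STS drops out of it instead of counting as a responder. The subgroup analyses use the imputed data only.

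**Working it through.** **Inputs.** Component scores and responder definition: SAP 9.1. HRCT schedule: SAP 3.1. Number randomized: 55, allocated 1:1 (SAP 4.1 and 4.2), so about 28 in an arm. The documents give no response rate and no missing-HRCT rate.

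**The plan's own figure.** Six components at -1, 0 or +1 give 6 × (-1) = -6 to 6 × (+1) = +6, as stated.

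**One subject.** FVC +1, DLCO +1, KSQ General Health 0, fatigue 0, steroid +1; HRCT missing. The five-component sum is +3.

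| HRCT, if known | Total | Category | Responder? |
|---|---|---|---|
| -1 | +2 | Partial Response | yes |
| 0 | +3 | Response | yes |
| +1 | +4 | Response | yes |

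Under the literal rule the score is missing and the subject is a non-responder.

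**All patterns.** Five components give 3^5 = 243 patterns.

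- Sum +5: 1 pattern; +4: 5 patterns; +3: 15 patterns. Total 1 + 5 + 15 = 21. Each keeps a total of at least +2 when HRCT is -1, so responder status is certain.
- Only the 1 + 5 = 6 patterns with a sum of +4 or more also guarantee the full Response category.
- If any +1 total with the steroid item at +1 counts as Partial Response, a sum of +2 that includes steroid +1 is also certain. The other four components must then sum to +1, which happens in 16 ways: 21 + 16 = 37.
- On that broader reading 75 patterns depend on HRCT and 131 can never be responders: 37 + 75 + 131 = 243.

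These counts give every pattern equal weight. They are not probabilities.

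**Weight of one subject.** 1/28 = 3.6 percentage points on that arm's rate.

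**Illustration; every input is an assumption.** Let p be the true response rate, m the fraction with HRCT missing (unrelated to response) and g the fraction of responders who are certain from five components.

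- Rate under the written rule: p(1 - m)
- Rate with the bounding rule: p(1 - m) + p·m·g
- Expected number misrecorded, equal m: 27.5 × (p1 + p2) × m × g

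With rates of 60% vs 30% or 50% vs 25%, m of 5–20% and g of 50–75%:

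- Low end: 27.5 × 0.75 × 0.05 × 0.50 = 0.5 of 55 subjects.
- High end: 27.5 × 0.90 × 0.20 × 0.75 = 3.7 of 55 subjects.

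With equal m the written rule shrinks the difference by the fraction m, here 5–20% of its true value. With unequal m the direction depends on which arm loses scans. For 60% vs 30% (true difference 30 points) and g = 75%:

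| Missing HRCT, active / placebo | Written rule | Bounding rule |
|---|---|---|
| 10% / 10% | 54.0 - 27.0 = 27.0 | 58.5 - 29.25 = 29.25 |
| 20% / 10% | 48.0 - 27.0 = 21.0 | 57.0 - 29.25 = 27.75 |
| 0% / 20% | 60.0 - 24.0 = 36.0 | 60.0 - 28.5 = 31.5 |

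**The case against.** The strongest reply is textual. Step 3 opens by limiting non-response to subjects whose data do not permit classification as responders, and five components summing to +3 do permit it. This stands in part: a programmer could follow that clause and spare these subjects. But the preceding sentence has already left the score missing, and the closing words equate missing with non-responder. The clause makes the paragraph inconsistent; it does not cure it. Two programmers could derive different Week 24 counts.

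A second reply is that the rule is prespecified and conservative, the study is exploratory, and listings will flag every subject with a missing component. That makes affected subjects visible, but it does not change the analysed result. Nor is the rule reliably conservative, as the 0%/20% row shows. Protocol 8.1 mentions independent adjudication of responder status, but the SAP gives it no role when a component is missing.

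Two stronger readings are tempting and are not supported.

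- A reader might infer that HRCT can never be filled. Early terminators are to have the Visit 8 procedures, which include HRCT (Protocol 11.10), and unscheduled imaging is captured (Protocol 8.1). Either could supply a rating.
- A reader might infer that the remote-visit provision makes late scans common. Protocol 11 says what to do when a subject cannot attend, not how often that happens. Extension entrants take their first open-label dose in clinic at Week 24, which narrows that route for them. Subjects who do not enter the extension are summarized in the double-blind phase only (SAP 4.3), so a late scan of theirs is not moved to the open-label phase.

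**Conclusion.** The point holds. On the literal derivation, a subject with no HRCT rating after LOCF and a five-component sum of +3 or more is coded a failure although the SAP's responder definition is met for every possible scan result. The certainty concerns responder status, that is Response or Partial Response; the full Response category needs a sum of +4.

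The logic rests only on the documents. The count is 21 of 243 patterns, or 37 on the broader reading of the steroid clause, which the SAP does not settle. The practical size is unknown, because it depends on how many Visit 8 scans are missing and in which arm. About 3.6 points per affected subject is firm arithmetic for an arm of 28; the 0.5 to 3.7 misrecorded subjects are an illustration under the stated assumptions. A reader might infer a substantial bias in the result, but nothing in the documents supports a particular share of subjects affected.

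**What to change.** Add to SAP 9.1, in place of the present wording on scores still missing after LOCF:

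> *If, after component-level LOCF, the responder status (Response or Partial Response versus Non Response) is the same for every possible value of the missing component(s), assign that status; otherwise impute non-responder.*

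Equivalently, set each missing component to -1 and count the subject as a responder if the definition is still met. The sentence must refer to two-level responder status. If it required the three-level category to be fixed, only 6 of the 37 patterns would qualify and the other 31 would still be coded as failures. SAP 9.1 should also say whether a +1 total with the steroid item at +1 always counts as Partial Response, since that decides between 21 and 37.

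No open-ended window for late scans is needed. If one is added, limit it to scans taken before the first open-label dose: after that dose a placebo subject has received active drug, and the cutoff in SAP 4.3 rightly keeps such data out of the randomized comparison.

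Make the change blind to treatment. If the blind is already broken, keep the written rule and report the bounding rule as a labelled sensitivity analysis. The cost is one sentence and a few lines of code. It needs no new data, and subjects whose status is truly undetermined remain non-responders.

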8.4. Approximate Number of Subjects

Approximately 100 subjects will be globally enrolled at approximately 75 sites.

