4.1. Sample Size

Formal sample size calculations were not performed. The sample size is based on recent literature of comparative studies ([Gibson et al., 1996](#); [Baughman et al., 2006](#); [Judson, 2014](#)) in sarcoidosis. There are 55 subjects randomized to this study.

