4.2. Randomization, Stratification, and Blinding

An interactive telephone/web response system will be used to allocate eligible subjects to each treatment group. Subjects will be randomized according to computer-generated allocation scheme to receive either Acthar Gel 1 mL (80 U) or placebo 1 mL administered twice a week in a 1:1 ratio. Both investigators and the subjects will be blinded to the treatment assignment. A block randomization will be performed.

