- Two baselines, baseline of overall study and baseline of active treatment, have been defined. Baseline of overall study is defined as the last assessment prior to the first dose of IMP at the double-blind treatment phase. Baseline of active treatment is defined as the last assessment prior to the first dose of active treatment in either the double-blind treatment phase or the open-label extension phase. All the analysis in the open-label extension phase that involves presenting change and/or percent change from baseline will present change/percent change from both baselines.
- Summary statistics will be provided for all study variables with descriptive statistics (number of subjects, mean, standard deviation (SD), median, minimum,

and maximum) for numerical (or continuous) variables. Frequency and percentages will be calculated for categorical variables.

- Unless specified otherwise for a given analysis, all statistical tests, when applicable, will be 2-sided with a significance level of 0.05.
- All data collected will be presented in listings, sorted by treatment group, subject identifier and date/time of procedure or event, if applicable.

All analyses will be conducted using SAS® Version 9.4 or higher. The Medical Dictionary for Regulatory Activities (MedDRA) version 23.0 will be used for coding adverse events (AEs), and medical and surgical histories. Prior or concomitant medication data will be coded according to the Anatomical Therapeutic Chemical (ATC) coding scheme of the World Health Organization (WHO) Drug Dictionary (Enhanced B2 dated March 2018 version, or higher) level 2 term.

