7.1. Demographics

Descriptive statistics will be provided for the following continuous variables collected at baseline:

- Age (year)
- Weight (kg)
- Height (cm)
- Body Mass Index (BMI) (kg/m^2) as recorded on the electronic case report form (eCRF)

The number and percentage of subjects will be provided for the following categorical variables:

- Sex (Male, Female)

- Race (American Indian or Alaska Native, Asian, Black or African American, Native Hawaiian or Other Pacific Islander, White, Multiple, Other)
- Ethnicity (Hispanic or Latino, Not Hispanic or Latino, Unknown, Unreported)
- Female Fertility Status (Surgically Sterile, Post-Menopausal, Childbearing potential)

A female fertility status listing will be provided for all randomized subjects.

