8.3.2. Treatment Compliance

During each visit, the number of injections that a subject was expected to take and the number of injections that a subject actually took since previous visit until prior to the current visit will be recorded on the eCRF.

Treatment compliance (%) of double-blind treatment phase is defined as:

$$\frac{(\text{Number of injections taken during double - blind treatment phase}) \times 100}{\text{Number of injections expected to be taken during double - blind treatment phase}}$$

Treatment compliance (%) of open-label extension phase is defined as:

$$\frac{(\text{Number of injections taken during the duration open - label extension phase }) \times 100}{\text{Number of injections expected to be taken during open - label extension phase}}$$

The study drug compliance rate in the double-blind treatment phase, and compliance rate in the open-label extension phase will be summarized by treatment group using the descriptive statistics. The compliance rates will also be summarized by categories (<80, 80 to <=120, and >120).

9. Efficacy Analysis

All efficacy evaluations will be conducted using the mITT population unless otherwise specified and will be provided by treatment group for the double-blind treatment phase. Efficacy evaluations will only be summarized descriptively using the open-label safety population by treatment group and total for the open-label extension phase. All summaries and analyses will be conducted on the observed values unless otherwise specified. All efficacy data will be presented in listings based on the mITT population in the double-blind treatment phase and based on the open-label safety population in the open-label extension phase. The derived efficacy variables will be displayed in data listings as well.

Additional subgroup analyses by sex, race and ethnicity will be performed on missing imputed data as specified. Other exploratory analyses may be performed as appropriate.

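### The STS subgroup analyses by sex, race and ethnicity have no treatment-by-subgroup interaction estimate, and the within-level tests they appear to plan are a poor guide to whether the effect differs.

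*SAP*

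**What the plan says.** At Week 24, SAP 9.1 gives STS responder proportions by arm, an odds ratio with an asymptotic 95% CI, and a Pearson "chi-square test (or Fisher's exact test if any expected count is less than 5) will be used to assess the comparability between treatment groups". For subgroups it adds: "Subgroup analyses by sex, race and ethnicity will be performed in similar manner as specified above on the imputed data only". The opening of SAP section 9 says much the same: "Additional subgroup analyses by sex, race and ethnicity will be performed on missing imputed data as specified".

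SAP 4.3 sets the level: unless specified otherwise, "all statistical tests, when applicable, will be 2-sided with a significance level of 0.05". No separate level or reading rule is given for subgroups.

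The only list of levels is in SAP 7.1, which describes the baseline tables: two for sex, seven for race, and for ethnicity "Ethnicity (Hispanic or Latino, Not Hispanic or Latino, Unknown, Unreported".

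The only interaction in the SAP is visit by treatment, in the repeated-measures model for DLCO and FVC (SAP 9.3 and 15.4). Protocol 15.5 plans subgroup analyses and says that further exploratory work may include logistic regression, but names no interaction with a subgroup factor. On size, SAP 4.1 records: "There are 55 subjects randomized to this study".

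**The concern.** A subgroup analysis asks whether the treatment effect differs between levels. A test within each level asks whether the effect is detectable there, and the answer depends heavily on how many subjects the level holds. With about 27 subjects per sex, an effect that is the same in men and women can easily cross 0.05 in one and miss it in the other.

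If the tables show a p-value per level and nothing that compares levels, a reader has little to stop the inference that the drug works in one sex only. At stake is how the subgroup tables of an exploratory trial are read. The overall Week 24 result does not depend on it.

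**Working it through.** The documents contain no power calculation, assumed effect or response rate, so there is no planned figure to reproduce.

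**Inputs**

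- 55 randomized (SAP 4.1) "administered twice a week in a 1:1 ratio" (SAP 4.2). Taken as 28 v 27, with all 55 in the mITT population.
- Missing responses count as non-response after component-level LOCF (SAP 9.1), so every mITT subject enters the tests.
- Test: Pearson, or Fisher if any expected count is below 5, two-sided 0.05 (SAP 9.1 and 4.3).
- Assumed: sexes evenly split, 14 v 14 and 14 v 13. The case series of 302 patients in Protocol 6.1 had 52% women, so this is plausible, but no split is given for this trial.
- Assumed: placebo response 30%, active response 30% to 70%, the same in both sexes.

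**Formula.** Let q1 and q2 be the within-sex probabilities of significance, enumerated exactly from binomials under the SAP's rule. Then:

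- exactly one sex significant = q1(1 − q2) + q2(1 − q1)
- both = q1·q2
- neither = (1 − q1)(1 − q2)

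| Active v placebo | q1 (14 v 14) | q2 (14 v 13) | Exactly one | Both | Neither |
|---|---|---|---|---|---|
| 30% v 30% | 0.024 | 0.038 | 6% | <1% | 94% |
| 40% v 30% | 0.054 | 0.068 | 11% | <1% | 88% |
| 50% v 30% | 0.145 | 0.171 | 27% | 2% | 71% |
| 60% v 30% | 0.308 | 0.350 | 44% | 11% | 45% |
| 65% v 30% | 0.414 | 0.461 | 49% | 19% | 32% |
| 70% v 30% | 0.528 | 0.577 | 50% | 30% | 20% |

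Worked case, 60% v 30%: 0.308 × 0.650 + 0.350 × 0.692 = 0.200 + 0.242 = 0.44.

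Beyond the peak the rate falls again, to 35% at 80% v 30%. With a 20% placebo rate the pattern is similar: 25% at 40%, 43% at 50% and 50% at 60%.

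**Uneven split.** One half is the peak for an even split only. At 70% v 30% the figure is 53% for a 60/40 split, 62% for 70/30 and 72% for 80/20.

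**What an interaction test would show.** In simulations of the same setting with identical effects in both sexes (even split, Wald test on the difference in log odds ratios with a 0.5 correction), the interaction was significant in 2.6% to 3.9% of trials.

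Its power is low. If the overall effect has standard error s, each half has s√2, and the difference between halves has √(2s² + 2s²) = 2s. With 80% overall power the standardized effect is 0.84 + 1.96 = 2.80. An interaction as large as the main effect therefore has 2.80/2 = 1.40 and power Φ(1.40 − 1.96) = Φ(−0.56), about 29%.

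**Very small levels.** The smallest two-sided Fisher p-value is:

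- 2 v 2: 2/6 = 0.33
- 3 v 3: 2/20 = 0.10
- 3 v 4: 1/35 = 0.029

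A level with 3 or fewer in both arms can never reach 0.05. One with 3 v 4 can.

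**The case against.** The case on the other side has four parts.

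- **The faulty comparison is the reader's, not the plan's.** Neither document says that subgroups will be compared by significance or used for a claim. The repeated analysis also includes proportions and an odds ratio with CI per level. This stands: half of a sound presentation is already planned, and the documents do not support a reading that the plan intends to infer sex-specific effects from p-values.
- **Within-level tests are not spelled out.** They follow from performing the analysis in a similar manner, and that is the natural reading, but it remains a reading.
- **The study is exploratory and allows further models.** Logistic regression and other exploratory analyses are permitted (Protocol 15.5, SAP section 9), so an interaction model could be run. This limits the consequence. It does not prespecify the estimate or say how to read the tables.
- **An interaction test would be weak.** This is correct, as the 29% above shows. It argues for reporting an estimate with its interval and against relying on the test alone. It does not make within-level p-values informative.

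A reader might also count 2 + 7 + 4 = 13 tests from SAP 7.1 and infer a large multiplicity problem. The documents do not support that count as a plan. The list serves baseline tables, several race levels may be empty among 55 subjects, and levels with 3 or fewer in both arms cannot be significant at all.

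**Conclusion.** The gap is real and modest. On the natural reading, SAP 9.1 tests treatment within each level at 0.05, and neither document plans an interaction test or estimate. With an identical true effect in both sexes, 55 subjects and an even split, exactly one sex is significant in 6% to about 50% of trials, depending on the true response rates.

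A reader might take the upper figure as the expected rate and conclude that half of such trials would mislead. The documents do not support that. The peak needs a true difference of about 35 to 40 percentage points and, as the figure for an even split, an even division of the sexes, and neither is stated. At a 10-point difference the rate is 11%, and at 20 points about 27%. At 60% v 30%, neither sex is significant (45%) about as often as exactly one is (44%).

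This is a worthwhile, inexpensive improvement to a secondary part of an exploratory analysis.

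**What to change.** Amend SAP 9.1, and the matching sentence in section 9, as follows:

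- Keep the responder proportions and the odds ratio with 95% CI per level. Drop the within-level p-values.
- Add one treatment-by-subgroup interaction estimate with 95% CI for each of sex, race and ethnicity. State that power is low at 55 subjects and that a non-significant interaction does not show a consistent effect.
- Pool sparse race levels before fitting, because a logistic interaction model with near-empty cells may fail to give finite estimates. Leave unknown and unreported ethnicity out of the comparison.
- Describe levels with 3 or fewer subjects in both arms by counts only.

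The cost is a few sentences in the SAP and one model per factor, with no new data. The downside is the low power of the interaction and slightly more analysis work. If the analyses have already been run, Protocol 15.8 provides for describing and justifying the departure in the study report.
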